### 7.3 Accrual, Follow-up, and Sample Size

The overall sample size for this project is 30. We anticipate recruiting 1-2 participants weekly for total study duration of 1.5-2 years (Table 2).

Order	Ν	Period 1	Period 2	Period 3
Sequence Placebo-CoQ10-NR (n=5)	10	A	В	C
Sequence Placebo-NR-CoQ10 (n=5)		A	C	В
Sequence NR-Placebo-CoQ10 (n=5)	10	В	A	С
Sequence NR-CoQ10-Placebo (n=5)		В	C	А
Sequence CoQ10-Placebo-NR (n=5)	10	С	A	В
Sequence CoQ10-NR-Placebo (n=5)		С	В	А

Table 2. Study design and sample size. Given the efficient cross-over design, 30 participants will receive each treatment by the end of the study.

Sample size was calculated based on values obtained from an standard deviation of the difference of VO2max on bicycle ergometry from a prior study of 2.1ml/kg/min. A total of 30 patients will enter this three-treatment crossover study. A total of 30 patients will enter this two-treatment crossover study. The probability is 80 percent that the study will detect a treatment difference at a two-sided 0.05 significance level, if the true difference between treatments is 2.1 (1 SD)ml/kg/min. This is based on the assumption that the standard deviation of the difference in the response variables is 2.1 ml/kg/min (Table 3). Sample size was calculated using the following sample size calculator: *http://hedwig.mgh.harvard.edu/sample\_size/js/js\_crossover\_quant.html* 

	VO2max Power	
Minimal detectable difference	80% (n)	90% (n)
0.5 SD	34	44
0.75 SD	16	21
1 SD	10	13

Table 3. Total samples size required to detect treatment effects for aerobic capacity bicycle ergometry from crossover design. Based on published study demonstrating the effect of a 12mo combined resistance and aerobic exercise program resulting in an increase of +5.7 ml/kg/min VO2peak with a standard deviation of the difference of 2. 1 ml/kg/min.

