# 2.3 Study Design

**Overview of study design:** This is a placebo-controlled, double-blind crossover trial with 3 arms: placebo, NR, and CoQ10. There are 2 phases 56 days each separated by a 1-week washout period.

A brief screening visit will assess eligibility criteria, and will include informed consent. Qualified participants will be randomly assigned (1:1) to 56 days of placebo followed by 7 days NR or CoQ10, followed another 7 day washout followed by 56 days of either NR or CoQ10. Qualified participants will participate in at least 4 study visits, plus a screening visit. An optional P MRS study visit to assess in vivo muscle mitochondrial phosphorylation capacity will be offered to those who qualify. Including the separate MRS visit will increase the total visits to 8. Study outcomes will be assessed at each of these 4 major visits.

Subjects will receive 1000mg of Nicotinamide riboside (Tru Niagen) or coenzyme Q10 (1200mg/day) for 8 weeks. This dose was chosen based on a review of studies in the literature evaluating biological activity. Placebo will consist of identical appearing tablet.

Objectives	Population	Exposure	Design	Outcome
Primary- To test if NR or CoQ10 supplementation improves aerobic capacity and muscle performance	Mod-severe CKD with eGFR < 50 mL/dL (N=30)	Randomized order CoQ10 or NR or Placebo	Placebo-controlled double-blind control crossover	VO2max and Work efficiency
Secondary- To test NR or CoQ10 on descriptive measures of mitochondrial and metabolic functioning	Mod-severe CKD with eGFR < 50 mL/dL (N=30)	Randomized order CoQ10 or NR or Placebo	Placebo-controlled double-blind control crossover	
 
-monocyte bioenergetics (Reserve capacity)
 
-ATPmax (MRS Imaging)
 
-Blood metabolomics & biomarkers
 
-Fatigue & Heart questionnaires
 

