### **Procedures/Sample collection:**

An overview of the study visit and procedures schedule is presented in Appendix I. Presented below is additional information on visit-specific study procedures and Table 4.

*Physiologic measurements from cycle ergometry:* The main outcome of this study is aerobic capacity (VO2max) using cycle ergometry. Secondary outcome is muscle performance using measures of total work and work efficiency which will be obtained by cycle ergometry using standard protocol measuring oxygen uptake starting at 0 watts (W) at 60 rotations per minute (rpm) increasing by 30W every 3 minutes until volitional exhaustion adapting a prior protocol used in CKD patients. Approximately 30W of activity is required for grocery shopping and 60W is necessary for household chores. Work efficiency will be calculated as the work performed/energy expended (VO2) above that in cycling 0 watts x 100%. The minimum criteria for a successful efficiency calculation will be a rating of perceived exertion (RPE) of 13 (scale 6-20) or 75% of predicted maximal heartrate. The minimum goal for successfully achieving a VO2max is a RPE of 17 or respiratory exchange ratio≥1. Recovery will consist of pedaling 5 minutes at 10 watts and 60rpm. **Participants should be fasting for at least 6 hrs prior to this test and not exercise for 48hr prior to this test.** 

*PBMC mitochondrial bioenergetic stress test:* Monocytes are specifically selected due the strong correlation of their bioenergetics properties with skeletal muscle and cardiac bioenergetics in the primate model. Blood samples will be process using an established protocol. Sample collection should be coordinated in advance with [name] ([contact]).

*Blood testing for metabolic response profile* (oxidative stress, inflammation, and plasma amino acids, metabolites, and electrolytes). Oxidative Stress and Inflammatory Biomarkers include: C-reactive protein and IL-6 levels will be determined using the automated Abbott FLX C-Reactive Protein Assay and by ELISA, respectively. Plasma

F2-isoprostanes and isofurans will be measured by GC-MS as described by Roberts and Morrow at Vanderbilt University (c/o [name]: [contact]).

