### 7.4 Random Assignment / Study Arm Assignment

Investigational drug services will be responsible for randomization of participants into the two treatment groups. Every effort will be taken to have an appropriate placebo pill appearing identical to study agent.

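### Section 7.3 claims 80% power for a 2.1 ml/kg/min difference with 30 patients, but its own Table 3 needs only 10; on the plan's inputs, 30 give more than 99.9% power, or 80% power for about 1.1.

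*Combined protocol and SAP*

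**What the plan says.** Section 7.3 sets the total at 30. It takes the SD of the difference in VO2max as 2.1 ml/kg/min and the true treatment difference as the same 2.1, that is, 1 SD. It then states: "The probability is 80 percent that the study will detect a treatment difference at a two-sided 0.05 significance level". The next sentence, which gives the SD assumption, cites Table 3.

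Table 3 is captioned "Total samples size required to detect treatment effects for aerobic capacity bicycle ergometry from crossover design". At 1 SD it gives 10 for 80% power and 13 for 90%. The other rows are 16 and 21 at 0.75 SD, and 34 and 44 at 0.5 SD. The caption takes the SD from a published study of a "12mo combined resistance and aerobic exercise program resulting in an increase of +5.7 ml/kg/min VO2peak".

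The number of patients behind each comparison is described in different ways:

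- Table 2 sets out six sequences of three periods, with five patients each. Its caption says "30 participants will receive each treatment by the end of the study".
- The section 7.3 text calls the study three-treatment, then says "A total of 30 patients will enter this two-treatment crossover study".
- Section 2.3 says "There are 2 phases 56 days each separated by a 1-week washout period".
- Section 7.4 says "Investigational drug services will be responsible for randomization of participants into the two treatment groups".
- The Schema gives the study size as 10 in each of three arms, and section 4.3 aims for 10 completers in each arm.

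**The concern.** The power sentence and Table 3 give different sample sizes for the same difference, SD, power and significance level: 30 in the text, 10 in the table. Thirty patients cannot give only 80% power where ten already do. Table 3 has no row for 30, which falls between its 80% entries of 16 (0.75 SD) and 34 (0.5 SD).

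This paragraph is the plan's only sample-size justification for its main outcome. As worded, it says the trial is sized for a difference of 2.1 ml/kg/min. If the inputs actually give 80% power for about half of that, a null result would be misread: true effects between roughly 1.1 and 2.1 would seem beyond the design's reach when, on the plan's own inputs, they are not. The sentence also hides how far the design depends on a borrowed SD. The mixed two- and three-treatment wording leaves the number of pairs per comparison unclear from the prose.

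**Working it through.** **Inputs (section 7.3).** Difference δ = 2.1 ml/kg/min; SD of the within-patient difference = 2.1; two-sided α = 0.05; n = 30, with every patient receiving every treatment (Table 2), so each active-placebo contrast has 30 pairs.

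**Method.** Paired t-test with df = n − 1 and noncentrality λ = √n × δ/SD. Power = P(|T| > t for α/2 and n − 1 df), where T is noncentral t with parameter λ.

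**Step 1: reproduce Table 3.** The smallest n reaching each power is:

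| Difference | 80% power | 90% power |
|---|---|---|
| 0.5 SD | 34 | 44 |
| 0.75 SD | 16 | 21 |
| 1 SD | 10 | 13 |

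All six entries match. Table 3 therefore rests on this method, and its entries are total patients. At n = 10 and 1 SD, λ = √10 = 3.16 and power is 80.3%.

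**Step 2: test the sentence by the same method.** At n = 30 and 1 SD, λ = √30 = 5.48 and power is 99.96%. The normal approximation gives Φ(5.48 − 1.96) = 99.98%.

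**Step 3: what 30 pairs detect with 80% power.** The solution is δ/SD = 0.529, so δ = 0.529 × 2.1 = 1.11 ml/kg/min. The normal approximation gives (1.960 + 0.842)/5.48 × 2.1 = 1.07.

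**Step 4: the SD that would make the sentence true.** 2.1/0.529 = 3.97, and 3.97/2.1 = 1.9 times the stated SD.

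**Step 5: other readings, keeping δ = 2.1.**

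| Reading | Power at 2.1 | 80% detectable difference |
|---|---|---|
| ANOVA residual df 56 (90 − 1 − 29 − 2 − 2) | 99.97% | 1.09 |
| α = 0.025 for two active-placebo contrasts | 99.86% | 1.24 |
| 2.1 read as a within-patient SD (SD of difference 2.1 × √2 = 2.97) | 96.3% | 0.529 × 2.97 = 1.57 |
| Placebo plus one active only (assumed 15 pairs per active) | 94.9% | 0.778 × 2.1 = 1.63 |

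A two-group parallel formula with 15 per group and SD 2.1 comes near the stated figure (78.2%, normal approximation). It contradicts the crossover design, the use of an SD of the difference, and Table 3.

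**Step 6: sensitivity.** The SDs above 2.1 and the 24 pairs are assumptions, not figures from the plan. The detectable difference is 0.529 × SD for 30 pairs and 0.597 × SD for 24.

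| SD of difference | 30 pairs: power at 2.1 | 30 pairs: 80% detectable | 24 pairs: 80% detectable |
|---|---|---|---|
| 2.1 | 99.96% | 1.11 | 1.25 |
| 2.5 | 99.4% | 1.32 | 1.49 |
| 3.0 | 95.9% | 1.59 | 1.79 |
| 3.5 | 88.8% | 1.85 | 2.09 |

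With 24 pairs, power at 2.1 is 99.7% at SD 2.1 and 80.4% at SD 3.5.

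**The case against.** The strongest defence is that the sentence describes ten patients per comparison. The Schema and section 4.3 both speak of ten per arm, and ten pairs give 80.3% at 1 SD, which is the stated figure. Thirty may simply be three times the Table 3 entry, although the plan does not say so. This probably explains the error but does not rescue the sentence. In the crossover of Table 2 all 30 patients contribute to each contrast, Table 3 labels its entries as totals, and the sentence speaks of 30. It does mean that the ten-per-arm wording should be clarified with the rest.

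A second objection is that the real margin may be much smaller than 99.96% suggests. The SD comes from a 12-month exercise programme. Section 4.3 expects some non-adherence and drop-out, and section 5.0 sets an effort standard for a valid test: "The minimum goal for successfully achieving a VO2max is a RPE of 17 or respiratory exchange ratio≥1". Taken together, an assumed SD of 3.5 and 24 evaluable pairs bring power at 2.1 down to 80.4%, almost exactly the plan's claim. This stands as a reason to show a joint range. It does not defend the sentence, which states its SD as 2.1 and its number as 30.

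Third, there are two active-placebo comparisons, and the plan states no multiplicity adjustment for them. At α = 0.025 the detectable difference is 1.24 rather than 1.11. The replacement text should say which level it uses.

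Finally, a careful reader can see from Table 3 that 30 patients detect slightly more than 0.5 SD, and the inconsistent design wording does not cause the arithmetic error. Both points are fair. They limit the weight of the concern but do not remove the contradiction.

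**Conclusion.** The concern holds. The power sentence in section 7.3 is wrong on its own inputs, and Table 3 is right. For 30 completers of all three periods, an SD of the paired difference of 2.1 and two-sided 0.05 per comparison, the plan should claim more than 99.9% power at 2.1 ml/kg/min, or 80% power at about 1.1. The stated 80% also fails if each participant has placebo and only one active treatment.

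The direction is benign: power is understated, and no analysis rule depends on the sentence. The result does not show that the trial has ample power in practice, because the SD and the number of evaluable pairs are both uncertain. It should be fixed as a certain error in a figure the plan relies on, but the trial's validity is not threatened.

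**What to change.** Replace the power sentence in section 7.3 with text such as:

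> With 30 participants completing all three periods, and assuming an SD of the paired difference in VO2max of 2.1 ml/kg/min, each active-versus-placebo comparison has 80% power to detect about 1.1 ml/kg/min and more than 99% power to detect 2.1 (two-sided 0.05 per comparison, not adjusted for the two comparisons). The SD is taken from a 12-month exercise study. If it were 2.5, 3.0 or 3.5, the difference detectable with 80% power would be about 1.3, 1.6 or 1.9 with 30 evaluable pairs, and about 1.5, 1.8 or 2.1 with 24.

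If an adjusted level of 0.025 is intended, give 1.24 in place of 1.1 and recompute the range.

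Keep only one of the two consecutive sentences on the number of treatments. If Table 2 stands as the design, the two-treatment sentence goes. Sections 2.3 and 7.4 must be reconciled with Table 2, so that the number of pairs per comparison is clear. State in the Schema and section 4.3 that ten per arm means ten per first-period treatment and 30 completers in all, if that is the intent.

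The cost is a text correction. Enrolment and Table 3 do not change.

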### 7.4 Random Assignment / Study Arm Assignment

Investigational drug services will be responsible for randomization of participants into the two treatment groups. Every effort will be taken to have an appropriate placebo pill appearing identical to study agent.

# 7.5 Blinding

Study participants, investigators, and research coordinators will be blinded to the study. The investigational drug pharmacy will receive a receive treatment/placebo designation in a sealed envelope on the day of study drug/placebo initiation. Subjects will not be told of their assignment. Early unblinding will occur to protect patient safety in the event of an adverse event that the investigator believes may be relate to treatment.

# 7.6 Data Analysis

# 7.6.1 Primary Analyses

The major assumption in the cross-over trial is that there is no carryover effect of first period into the second period. The assumption is that a 1-week washout combined with a 2 month treatment will be sufficient to eliminate any potential carryover effect. The statistical model we assumed for continuous data from the  $3 \times 3$  crossover trial. We will use ANOVA to estimate sequence effects, treatment effects, and period effects. Given the short half-life of these drugs, we estimate that the drug washout will occur over 1 week with any residual effects by 3 weeks. According to this model, the coefficient of the interaction term between the treatment and time represents the treatment effect.

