# **Secondary Analyses**

We will assess differences in plasma metabolites using a linear mixed model approach with random intercepts, in which the log-transformed metabolite will be regressed on treatment type (Placebo vs Coenzyme Q10 or NR), time point (pre vs post) and the interaction of the two. We will use metaboanalyst to conduct pathway enrichment analysis.

For differential analysis of transcriptomic data, paired analyses of pre- and posttreatment with NR or CoQ10 compared to pre- and post- treatment with placebo will be performed using Significance Analysis of Microarrays (SAM) method implemented in Multi Experiment Viewer (MeV) application (Saeed et al. 2006; Saeed et al. 2003). Genes differentially expressed between two groups with a q-value (False Discovery Rate) below 0.05 were considered significant.

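### The primary VO2max ANOVA names no participant effect or within-person error term; fitted as listed, it would not use the variance on which the trial is sized

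*Combined protocol and SAP*

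**What the plan says.** Section 7.6.1 holds the whole primary analysis. On the model it says "We will use ANOVA to estimate sequence effects, treatment effects, and period effects". The sentence before it, which should introduce the model for the 3 × 3 crossover, breaks off without a verb, and no equation follows. The last sentence of the section places the treatment effect in an interaction of treatment with time, a term that is not among the three listed effects.

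A participant-level term appears once in the statistical sections. The Secondary Analyses section will study plasma metabolites "using a linear mixed model approach with random intercepts". Nothing similar is said for VO2max.

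Section 7.3 plans 30 participants in six sequences of five over three periods. The sizing assumes that "the standard deviation of the difference in the response variables is 2.1 ml/kg/min", tested "at a two-sided 0.05 significance level". Section 7.2 describes the primary endpoint as a change in aerobic capacity, and the visit schedule includes one baseline VO2max test before the three end-of-period tests.

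**The concern.** Each participant contributes three end-of-period VO2max values. A crossover is efficient because each person's stable level is removed before treatments are compared, and the SD in 7.3 is of that kind. A sequence term does not do this job: it removes only the average level of each group of five and leaves the differences among the five in the error.

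Two analysts could therefore read 7.6.1 and report standard errors that differ by a factor of 1.4 to more than 4. The literal reading could miss a real drug effect. It could also report a sequence effect that does not exist, which readers might take as carryover in a trial whose stated major assumption is that there is none.

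**Working it through.** **Inputs from the documents.** Section 7.3: SD of the within-person difference 2.1; two-sided 0.05; 30 participants, six sequences of five, three periods. Section 7.6.1: effects named are sequence, treatment and period.

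**Input not in the documents.** The between-person SD of VO2max, σb. I use 1.5, 3, 5 and 7 ml/kg/min. With the within-person SD derived below, these imply within-person correlations of about 0.5, 0.80, 0.92 and 0.96.

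**Step 1: reproduce Table 3.** A paired t-test (noncentral t, n − 1 degrees of freedom) gives the following n at 80% / 90% power:

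- 0.5 SD: 34 / 44
- 0.75 SD: 16 / 21
- 1 SD: 10 / 13

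All six cells match, so the sizing is within-person.

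**Step 2: within-person SD per visit.** σw = 2.1/√2 = 1.485, so σw² = 2.205.

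**Step 3: standard error with a participant term.** Residual df = 90 − 1 − 2 − 2 − 29 = 56. SE = √(2 × 2.205/30) = √0.147 = 0.383.

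**Step 4: standard error with only the three listed effects.** Residual df = 90 − 1 − 2 − 2 − 5 = 80. Of these, 24 (30 participants − 6 sequences) carry variance σw² + 3σb², and 56 carry σw². The expected error mean square is

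[24(σw² + 3σb²) + 56σw²]/80 = σw² + 0.9σb².

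The reported SE is then about √(2(σw² + 0.9σb²)/30):

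- σb = 1.5: √(2 × 4.230/30) = 0.53
- σb = 3: √(2 × 10.305/30) = 0.83
- σb = 5: √(2 × 24.705/30) = 1.28
- σb = 7: √(2 × 46.305/30) = 1.76

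The mean SE in simulation is slightly lower (table below). The true sampling SD of the estimate stays near 0.38 throughout, because with complete balanced data the estimate is the same within-person contrast either way.

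**Step 5: the same model on change from baseline.** Subtracting one baseline value cancels the stable person level, but its error is shared by all three change scores. Taking baseline error equal to visit error, σb is replaced by 1.485: √(2 × (2.205 + 0.9 × 2.205)/30) = √(2 × 4.190/30) = 0.53, whatever the between-person SD.

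**Step 6: power and the sequence test.** Simulation of the six-sequence design:

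| Analysis | Mean SE | Power at 1.1 | Power at 2.1 | Sequence test, true null rejected |
|---|---|---|---|---|
| With participant term | 0.38 | 80% | >99% | – |
| Three effects, change scores | 0.53 | 55% | >99% | 37% |
| Three effects, raw, σb 1.5 | 0.53 | 55% | >99% | 37% |
| Three effects, raw, σb 3 | 0.82 | 11% | 86% | 55% |
| Three effects, raw, σb 5 | 1.27 | 0.2% | 20% | 60% |
| Three effects, raw, σb 7 | 1.74 | 0% | 1% | 61% |

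Across repeated simulations the last column ran from about 36% to 62%. The difference of 1.1 ml/kg/min is about what 30 participants detect with 80% power (0.53 SD × 2.1 = 1.11). With the participant term the type I error for treatment is about 5%. Without it, it is 0.8% at a correlation of 0.5 and 0.02% at 0.8.

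The sequence test is too liberal because its numerator has expectation σw² + 3σb² under no sequence effect, while its denominator has only σw² + 0.9σb². At σb = 3 that is 29.205 against 10.305.

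**The case against.** The strongest reply is that 7.6.1 lists effects to be estimated and does not set out a full model. It refers to a crossover model, and a usual crossover ANOVA carries participants within sequence. A reader might infer that the 90 values will be treated as independent, or that a between-person comparison will replace the within-person one. The documents support neither. The error term is unspecified, and with complete balanced data the estimate is the within-person contrast in both cases. This reply stands, and it limits the point to an omission.

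Second, section 7.2 describes the endpoint as change. If change scores are analysed, the severe raw-value figures do not arise. This also stands, but a standard error of 0.53 in place of 0.38 and power of 55% in place of 80% at 1.1 ml/kg/min remain.

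Third, a reader might infer that the planned effect of 2.1 ml/kg/min would be missed. That does not follow in general. Thirty participants exceed the 10 that Table 3 requires for 1 SD, so power stays at 86% or more for change scores, and for raw values up to σb of 3. It falls below that at higher values: 36% at a correlation of 0.9 (σb = 1.485 × √(0.9/0.1) = 4.5) and 20% at σb of 5.

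Fourth, it is tempting to add that this ANOVA would discard participants who miss a period. A three-term least-squares fit uses every available row, so it would not. With missing periods, however, the treatment estimate itself depends on whether participant is modelled, and section 4.3 expects drop-out.

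Last, the plan attaches no decision to the sequence result. The harm there is one of interpretation.

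**Conclusion.** The point holds as an omission with consequences. Section 7.6.1 does not name the term that would make the primary analysis match the sizing in 7.3, and nothing else in that section supplies it. Taken literally, the plan gives a treatment standard error about 1.4 times too large at best (0.53/0.38), for change scores or raw values with σb of 1.5. At worst in the range tried it is about 4.6 times too large (1.74/0.38). The error is conservative for treatment: it creates no bias with complete balanced data and no false-positive drug effect. For sequence it runs the other way.

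The change-score figures need no between-person SD, but they assume an additive person effect and baseline error equal to visit error. The raw-value figures rest on an assumed σb, and those at σb of 5 and 7 should be read as the upper part of that range.

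**What to change.** In 7.6.1, replace the ANOVA sentence and the incomplete sentence before it with a stated model: a linear mixed model for end-of-period VO2max, with fixed effects for treatment (three levels), period and sequence and a random participant effect, using all available periods. Report the NR-placebo and CoQ10-placebo contrasts with 95% confidence intervals. Test sequence against between-participant variation.

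Also delete the sentence that equates the treatment effect with a treatment-by-time interaction, or reconcile it with the model; left in place it would contradict the new text. Say how the change wording in 7.2 maps to this model. With complete data, subtracting a single baseline does not alter the treatment contrasts once participant is in the model.

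The cost is a few sentences. No new data, visits or participants are needed, and the plan already uses random intercepts for the metabolites. With complete balanced data, an ANOVA with participants within sequence would give the same treatment contrasts; the mixed model handles missed periods more readily.

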# Baseline visit and Post-treatment visits (2, 3, 4)

The participant will have been required to fast for at least 6 hrs prior to each visit and abstain from caffeine or smoking before bicycle ergometry testing. Patient should avoid exercise 48hours prior to cycle ergometry. Treatment will be dispensed after cycle

ergometry at baseline and post-treatment visits 2,3 and 4. The following data will be obtained:

- Vital signs.
- Fasting blood collection for banked plasma and peripheral blood mitochondrial energetics.
- Anthropometrics (height and weight and waist to hip ratio)
- Urine pregnancy test will be given to women of child-bearing potential
- Resting energy expenditure (REE) and cycle ergometry will be performed at the Prevention center.
- The optional MRS and Muscle Fatigue tests will occur at the diagnostic imaging center at UWMC at baseline and in the same week of visits 2, 3 and 4 while patient remains on study drug. Patient should wait avoid heavy exercise for 48hrs before MRS.
- Questionnaires will be administered (PROMIS fatigue short form 17, PROMIS physical function short form 20a, and Kansas city heart failure questionnaire)

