# Blood Collection:

- NAD samples will be obtained from fasting whole blood collected in one 2.7ml Blue (sodium citrate tube). From the blue tube, after inversion mixing, 0.5ml will be pipetted into 2 cryotubes **on dry ice.** Samples will be immediately frozen on dry ice and placed in -80C ASAP. Samples will be sent to [name] in clinical pharmacology ([contact]).
- EDTA Plasma samples will be sent to University of California at Davis West Coast Metabolomics for liquid chromatography high-resolution mass spectrometry (LC-MS) for targeted metabolomics analysis. We will perform additional transcriptomics using mRNA samples obtained from Paxgene tubes which will also be sent to West Coast Metabolomics.
- Paxgene mRNA will be obtained at baseline and post-intervention visits.
- Clinical laboratory assays for determination of comprehensive metabolic panel (electrolytes, blood urea nitrogen, creatinine, glucose, albumin, total protein, calcium, alkaline phosphatase, ALT, AST, total bilirubin), CPK, lactate, triglyceride will be performed at the *KRI Core Research laboratory*.

*Urine collection:* **Spot urine** for metabolomics will be collected at baseline and after each treatment period (visits 2-4).

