# Week 6, 13, 20 (Visit 2, 3, 4):

The prevention center and [name] lab will be contacted to arrange the primary outcome of resting energy expenditure, aerobic capacity and secondary outcomes of monocyte mitochondrial energetics at the end of each treatment period. Patients will also have fasting blood collection and return a 24hr urine collection. If qualified, they will also receive a repeat MRS at UWMC during the same week. **Patient remain on treatment during these visits to ensure drug effect.** 

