# Washout (week 7 and 14):

After the second visit, the participant will undergo a 1 week washout period prior to initiating the subsequent treatment arm for another 6 week period.

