## 7.2 Endpoints

Primary endpoints are change in aerobic capacity using cycle ergometry. Secondary endpoints are change in muscle work efficiency, metabolic response profile and markers of oxidative stress and inflammation.

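### Section 7.6.1 defines the primary treatment effect in two conflicting ways: as the ANOVA treatment effect, and as a treatment-by-time interaction that the ANOVA lacks and whose time is undefined

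*Combined protocol and SAP*

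**What the plan says.** Section 7.6.1 (Primary Analyses) names the model by its effects: "We will use ANOVA to estimate sequence effects, treatment effects, and period effects". It closes with: "According to this model, the coefficient of the interaction term between the treatment and time represents the treatment effect". Time is not defined there. The Secondary Analyses section also uses a treatment-by-time interaction, with time coded as pre or post. It does so only for log-transformed metabolites, and does not say which measurement is the pre value in periods 2 and 3.

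Section 7.2 states "Primary endpoints are change in aerobic capacity using cycle ergometry", without naming the value from which change is taken.

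On timing, Section 2.3 says "Study outcomes will be assessed at each of these 4 major visits". Table 1 places these visits at baseline and at weeks 6, 13 and 20, the ends of the three periods. For the last three, Section 5.0 adds "Patient remain on treatment during these visits to ensure drug effect". After the visit, "the participant will undergo a 1 week washout period prior to initiating the subsequent treatment arm"; no VO2max test is scheduled between washout and the next period. Table 2 (Section 7.3) gives six sequences of five participants, so each participant receives all three treatments.

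**The concern.** In this design the drug effect is the treatment main effect: each participant's end-of-period value on NR (or CoQ10) against the same participant's value on placebo, adjusted for period. The ANOVA in Section 7.6.1 supplies that contrast. The closing sentence points to a different coefficient, in a model that is not written down.

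A pre/post interaction would need a pre-treatment value for each period. Here only period 1 has an off-drug one. For periods 2 and 3 the analyst must reuse the study baseline, take the previous on-drug visit, or read time as period, and the plan does not say which. The sentence also speaks of a single coefficient, although there are two active-versus-placebo comparisons.

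The primary result is at stake. If the choice is left until data are in hand, the estimate can be selected after the results are seen.

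**Working it through.** **Inputs.** Section 7.3: 30 participants, six sequences of 5, two-sided alpha 0.05, SD of the within-person difference 2.1 ml/kg/min, planned difference 2.1. Assumed: complete data, constant drug effect, no carryover.

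**Step 1: the plan's own figure.** A paired t test with n − 1 degrees of freedom, with power taken from the noncentral t with noncentrality (difference/SD) × √n, gives 34/44, 16/21 and 10/13 for 0.5, 0.75 and 1 SD at 80%/90% power. This matches Table 3 exactly and confirms that 2.1 is used as the SD of a within-person difference. The same formula at n = 30 gives 80% power at 1.11 ml/kg/min.

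**Step 2: is the interaction in the stated model?** For the 90 end-of-period values, the design matrix with sequence, period and treatment has rank 10. Adding treatment-by-period raises it to 14. The interaction is therefore four extra parameters outside the listed ANOVA. With noise-free data and a true effect of 2.1 for both products, the treatment coefficients are 2.1 and all four interaction coefficients are 0.

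**Step 3: the ANOVA contrast.** Visit-level variance = 2.1²/2 = 2.205. SE = √(2 × 2.205/30) = √0.147 = 0.383. Analytic power is 81.2% at 1.11 and 99.97% at 2.1.

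**Step 4: what the interaction estimates under different codings.** NR versus placebo, participant effects fitted, 60,000 simulated trials per main scenario (20,000 for a). The list is illustrative, not complete.

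| Coding | Mean estimate at true 2.1 | Model SE | Type I error | Power at 1.11 | Power at 2.1 |
|---|---|---|---|---|---|
| ANOVA treatment contrast | 2.10 | 0.38 | 5.1% | 81% | >99.9% |
| (a) time = period, linear term | 0.01 | – | – | – | rejects 5.2% |
| (b) pre = previous visit | 2.80 | 0.50 | 11% | – | – |
| (c) pre = baseline copied into each period | 2.10 | 0.48 | 1.5% | 66% | 99.8% |
| (d) baseline once, treatment acts only after it | 2.10 | 0.38 | 5.0% | 82% | – |
| (e) baseline once, labelled with the period-1 treatment | 2.09 | 0.855 | 5.0% | 25% | 68% |

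- **(a)** The joint 4-df test rejects 5.3% at a true NR effect of 2.1. The term measures variation of the effect across periods, not the effect.
- **(b)** Write tN and tC for the two drug effects and b for the off-drug mean. The average pre value is b + tC/3 before NR and b + (tN + tC)/3 before placebo. The contrast is therefore tN − tC/3 + (tN + tC)/3 = (4/3)tN, and 4/3 × 2.1 = 2.80. Under the null the true SD is 0.63 against a model SE of 0.50. If only CoQ10 works (2.1), NR is falsely positive in 8.5%.
- **(c)** One measurement is counted three times. The true SD is 0.38 but the model reports 0.48. This fit omits period; adding it leaves power at 1.11 at about 65%.
- **(e)** This fits treatment, time and their interaction, the three terms listed in Secondary Analyses. The pre difference then rests on 10 participants per treatment: SE = √(0.147 + 2 × 2.205 × (4/3)/10) = √0.735 = 0.857, about 2.2 times the ANOVA value.

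Random-intercept REML fits (150 trials each, between-person SD 3 and 5) give the same picture: SE 0.38 for the ANOVA contrast and for (d), 0.85 for (e).

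**The case against.** The strongest reply is that the text points to a harmless reading. Section 7.2 speaks of change, Secondary Analyses codes time as pre or post, and the blood-collection text separates baseline from later visits ("Paxgene mRNA will be obtained at baseline and post-intervention visits"). Pre would then be the study baseline. Under that reading, (c), (d) and (e) are all unbiased, and (d) makes the disputed sentence correct. A competent analyst would in any case report the ANOVA treatment effects that the section promises. The sentence meant to introduce the model is also incomplete, so wording may have been lost in drafting or in reading the PDF.

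Part of this stands. Coding (b) is the less likely one, (a) is an unlikely deliberate choice, and (c) does not change the conclusion at the planned 2.1. Lost text cannot be excluded.

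It does not settle the matter. The listed effects still include no interaction, and time is still undefined. Coding (d) is right only in a model other than the stated ANOVA. Choosing the study baseline is not enough either: (e) also uses it once, and power at 2.1 falls to 68%. A primary estimate should not depend on the analyst ignoring the section's last sentence.

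The absolute powers rest on the SD of 2.1, which Table 3 takes from a 12-month exercise study, and on complete data, although Section 4.3 allows for drop-out. The 4/3 ratio, the SE ratios and the type I errors when neither drug works do not depend on the value 2.1.

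**Conclusion.** The concern holds and should be settled before the data are analysed. Section 7.6.1 gives two definitions of the primary effect that coincide only under a coding it does not state. The ANOVA contrast and (d) agree and are correctly calibrated. The other codings either do not estimate the drug effect (a), overstate it by a third with about twice the nominal false-positive rate (b), or are unbiased but less powerful (c, e). The loss under (c) matters only near 1.11 ml/kg/min; the loss under (e) matters at the planned 2.1. These sizes assume 30 completers, a constant effect, no carryover and SD 2.1. The inconsistency in the text needs none of these assumptions.

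**What to change.** 1. Delete the interaction sentence in Section 7.6.1 and complete the unfinished model sentence.
2. Define the primary estimates as NR minus placebo and CoQ10 minus placebo, from a model of end-of-period VO2max with sequence, period and treatment as fixed effects and participant as a random effect (or nested within sequence). With fixed participant effects alone the planned sequence effect cannot be estimated: the participant columns have rank 30, and adding sequence leaves it at 30.
3. State how the single baseline is used. If it enters as a response, say that it enters once and that treatment acts only after it. The word change in Section 7.2 can stay: change on NR minus change on placebo, both from the same baseline, equals end-of-period NR minus placebo.
4. In Secondary Analyses, use the same end-of-period contrasts for metabolites and transcripts, keeping SAM and the q-value rule, or define pre as in item 3.
5. Label any treatment-by-period or carryover term a sensitivity check.
6. Reconcile the MRS timing under Optional Procedures and Exploratory Endpoints, which refers to a visit 6, with the schedule in Table 1.

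The cost is wording only: no new data, visits or participants.
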